Study population: patients with RAS wild-type unresectable, advanced/recurrent colorectal cancer refractory or intolerant to fluoropyrimidines, oxaliplatin, irinotecan and angiogenesis inhibitors (bevacizumab, afibbercept, ramycirumab, etc.)

Planned number of subjects:

A maximum of 58 subjects

CONFIDENTIAL

Number of study sites:

Phase I part: approximately 5

[figure not shown]
Phase II part: approximately 30

Method of administration:

Treatment for 4 weeks (28 days) as 1 course according to the dosage, schedule and route of administration as follows.

Panitumumab: 6 mg/kg/dose once each on Day 1 and Day 15 by IV administration (IV drip infusion)

TAS-102: 35 mg/m²/dose given orally twice daily (after breakfast and after dinner) for 5 consecutive days followed by 2 days of washout and after this is repeated twice, 14 days washout will be implemented.

If either panitumumab or TAS-102 or both drugs are to be reduced for DLT occurrence in phase I part, dosage and administration will be as follows.

If panitumumab is to be reduced: 4.8 mg/kg/dose once each on Day 1 and Day 15 by IV administration (IV drip infusion)

If TAS-102 is to be reduced: 30 mg/m²/dose given orally twice daily (after breakfast and after dinner) for 5 consecutive days followed by 2 days of washout and after this is repeated twice, 14 days washout will be implemented.

Dose limiting toxicity (DLT) definition

In this study, DLT will be assessed based on the adverse events observed in 6 subjects at maximum enrolled in phase I part. DLT will be defined as follows [definition and grade will be based on Common Terminology Criteria for Adverse Events (CTCAE) ver4.03]. Further, DLT will be assessed from Day 1 of course 1 of protocol treatment, and if DLT does not occur by Day 1 of course 2, it will be handled as no occurrence of DLT in the subject. Adverse events that can clearly be denied of causal relationship with the protocol treatment will not be assessed as DLT. If serious adverse event or unexpected adverse event occurs which causal relationship with the protocol treatment cannot be denied other than the following, it may be determined as to whether or not to handle it as DLT in consultation with the Investigator, the Research Steering Committee and the sponsor.

1. Persistent Grade 4 neutropenia for more than 7 days under maximum supportive therapy
2. Febrile neutropenia
3. Blood platelet decreased of Grade 3 requiring platelet transfusion or blood platelet decreased of Grade 4

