8.0 PROTOCOL TREATMENT

The protocol treatment, contraindicated drugs/therapies, and recommended supportive care/combination therapies in this study are explained in this section. The drugs used for this study should be ethical drugs used by the study site. See the latest package insert for details and handling of each drug.

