8.5 Criteria for protocol treatment change

8.5.1 Criteria for suspension/dose reduction of panitumumab

The criteria for suspension/dose reduction and doses of panitumumab are shown in Table 8.f and Table 8.g, respectively.

Table 8.f Criteria for suspension/dose reduction of panitumumab

Item	Grade	Dose adjustment for the next dose of panitumumab
Skin disorder	≥ 3	Dose reduction by 1 level after suspension However, treatment at a dose of 6 mg/kg is allowed without dose reduction when it recovers to Grade 2 or less within 6 weeks (42 days) .
Hypomagnesaemia *	≥ 3	
Pulmonary fibrosis (interstitial pneumonia)	≥ 2	Discontinue protocol treatment
Infusion reaction (reaction from injection) **, ***	≥ 3	Discontinuation (no resumption)

Dose reduction/suspension is allowed as necessary at the discretion of the investigator or the subinvestigator due to adverse events not listed above.

*: When accompanied by abnormal ECG findings requiring treatment such as significant QTc prolongation, discontinuation or suspension of panitumumab should be considered irrespective of the severity of hypomagnesaemia.

**: Allergic reaction, anaphylactoid reaction, and chills, fever, and dyspnea occurring within 24 hours after the initial dose

***: If infusion reaction is observed, immediately discontinue administration. The course may be resumed at the discretion of the study site. In the event that Grade 1 or 2 infusion reaction occurs during infusion, careful administration will be allowed after appropriate supportive therapy has been given or infusion speed has been decreased by 50%, etc., upon administration of subsequent course.

Table 8.g Doses of panitumumab

Dose reduction level	Panitumumab
Initial dose	6 mg/kg
-1	4.8 mg/kg
-2	3.6 mg/kg
-3	Discontinuation (no resumption)

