8.7 Criteria for discontinuation of protocol treatment for each subject

The number of doses is not specified. However, protocol treatment should be discontinued when any of the criteria for discontinuation of protocol treatment listed below is met. The date of discontinuation of protocol treatment is defined as the date when the investigator or the subinvestigator decides on discontinuation of protocol treatment. The investigator or the subinvestigator should record the main reason for discontinuation of protocol treatment in the case report form (hereinafter referred to as CRF) according to the classification described below. For subjects discontinuing before enrollment, see 9.3 Records of subjects who discontinued before enrollment.

1. Lack of efficacy (exacerbation)

When PD is evident in the clinical or imaging evaluation

2. Adverse event

Discontinuation of treatment due to an adverse event in the opinion of the investigator or the subinvestigator, or according to the protocol treatment discontinuation criteria. However, death during protocol treatment will be classified in “4. Death during protocol treatment” and not in this item.

Protocol treatment is postponed due to adverse event for 58 days or more after the day of starting the last course. However, postponement due to holidays is allowed.

3. Voluntary discontinuation

A subject wishes to discontinue study participation. The reason for discontinuation should be recorded in CRF when it is clarified.

CONFIDENTIAL

Note: Attempts should be made as best as possible to clarify the reason for voluntary discontinuation. (Discontinuation due to adverse event or lack of efficacy should not be classified as “voluntary discontinuation”).

4. Death during protocol treatment

Death before discontinuation of protocol treatment is decided. Date of death, reason of death (protocol treatment related, primary disease, others) should be described in the CRF.

5. Significant deviation from the protocol

When study continuation may cause intolerable risk to the health of a subject because the subject was found not to satisfy the inclusion criteria specified in the protocol after enrollment or the protocol has not been observed.

6. Lost to follow-up

When subject fails to make visits and cannot be contacted. The attempts that were made to contact the subject should be recorded in the source documents.

7. Discontinuation of the entire study

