8.12 Recommended supportive care and combination medications

The supportive care and concomitant medications shown below are recommended during the study period (from obtaining consent until discontinuation of protocol treatment). The absence of supportive care or concomitant medications does not constitute a protocol deviation.

- Neutropenia
Granulocyte colony stimulating factor (hereinafter referred to as G-CSF) should be administered. The type of G-CSF products administered should depend on the insurance coverage.
- Nausea/vomiting
Premedication including prophylactic administration of antiemetics is allowed. Premedication with 5-HT3 (serotonin) receptor antagonists, NK1 (neurokinin 1) receptor antagonists, steroids, and antihistamines may be carried out using the method employed at each study site.
- Diarrhoea
Fluids and electrolyte balance will be followed adequately, and suitably supplemented, as necessary. If careful observation suggests that it is necessary, administration of an antidiarrheal such as loperamide hydrochloride may be considered.
- Allergic reaction
Treatment with adrenal corticosteroids, antihistamines, etc. may be considered at the time of onset or for premedication at the start of the subsequent course. Careful administration of panitumumab by slowing the infusion speed may be considered.
- Pulmonary fibrosis (interstitial pneumonia)
If it occurs, it should be treated according to the severity (e.g., steroid pulse therapy).
- Hepatitis B
Refer to JSH Guidelines for the Management of Hepatitis B virus infection (http://www.jsh.or.jp/doc/guidelines/HBV_GL_ver2.201406.pdf) and take appropriate action and monitoring.
- Others
Drugs for treatment of adverse events may be coadministered at the discretion of the investigator or the subinvestigator. Symptomatic therapies which have been continued from before the start of this study are allowed.

In addition, it is recommended that the supportive care shown below be performed at the discretion of the investigator or the subinvestigator when any of panitumumab-related adverse events listed below is observed. The absence of supportive care does not constitute a protocol deviation.

- Skin disorder
 - Tetracycline antibiotic (e.g. oral minocycline)

CONFIDENTIAL

- External salicylic acid petrolatum (10%)
- External steroid therapy (example)
 - Face: hydrocortisone butyrate (0.1%)
 - Trunk: difluprednate (0.05%)
- Moisturizer (example): heparin analog lotion

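### Table 8.f's definition of infusion reaction leaves Grade 3 or higher chills, fever or dyspnea after a later panitumumab infusion outside the mandatory stop

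*Protocol*

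**What the plan says.** Protocol Section 8.5.1, Table 8.f, has a row for infusion reaction. At Grade 3 or higher, panitumumab is discontinued and may not be restarted. The row carries no time limit.

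The two-asterisk footnote to that row defines the event: "Allergic reaction, anaphylactoid reaction, and chills, fever, and dyspnea occurring within 24 hours after the initial dose". Neither the protocol nor the SAP defines it anywhere else. Both protocol versions in the file carry the same footnote.

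The three-asterisk footnote gives the handling: "If infusion reaction is observed, immediately discontinue administration. The course may be resumed at the discretion of the study site". It continues: "In the event that Grade 1 or 2 infusion reaction occurs during infusion, careful administration will be allowed", subject to supportive therapy or a slower infusion at the subsequent course.

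Events outside the table fall under its closing line: "Dose reduction/suspension is allowed as necessary at the discretion of the investigator or the subinvestigator due to adverse events not listed above".

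**The concern.** A mandatory stopping rule is only as wide as the definition behind it. Here the rule is meant to govern the next panitumumab dose, whichever dose that is, but three of the listed signs are tied to the initial dose. A subject with Grade 3 or higher dyspnea after, say, the Day 15 infusion of Course 1, whom the site does not label as allergic or anaphylactoid, does not meet the definition as written. The permanent stop is then not triggered, and re-exposure becomes a matter of judgement.

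What is at stake is patient safety on re-exposure and consistent handling of the same event. Nothing in the efficacy analysis depends on it.

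**Working it through.** This is mainly a check of text against text, with a short calculation for size.

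**1. How many infusions come after the first.** Table 8a gives panitumumab on Days 1 and 15 of each 28-day course, and Section 8.7 sets no limit on the number of doses. The study summary gives 6 months as a guide to treatment duration, and SAP 7.2.3.1 takes 6 months as 168 days.
- Courses: 168 / 28 = 6. Planned infusions: 6 × 2 = 12. After the first: 12 − 1 = 11.
- This assumes a subject who completes six courses on schedule. It is a count of planned infusions and says nothing about when reactions occur.

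**2. Possible readings of the footnote.**
- *Time limit applies to chills, fever and dyspnea only.* Allergic and anaphylactoid reactions are covered at every infusion; the three symptoms are covered only after the first. This is the reading taken here.
- *Time limit applies to the whole list.* Later allergic and anaphylactoid reactions also drop out, so the gap is wider.
- *Initial means the first dose of each course.* Section 8.3 uses the word in that way for TAS-102. Day 15 of every course is still left out: 6 of the 12 planned infusions.
- *Initial means the starting dose level, as in Table 8.g.* Infusions at 4.8 or 3.6 mg/kg are still left out.

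The gap varies in width, but none of these readings closes it.

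**3. Does the rest of the protocol limit infusion reaction to the first dose?** No. The Table 8.f row has no such limit. Section 9.2.5 lists infusion reaction among the symptoms to be confirmed at medical examination, and Tables 9.a and 9.b make clinical findings mandatory on Days 1 and 15 of second and later courses. The footnote is out of step with both.

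**4. Is there another mandatory stop for the uncovered case?**
- Table 8.d (starting panitumumab) names only skin symptoms and hypomagnesaemia; anything else is discretionary.
- The closing line of Table 8.f (quoted above) is discretionary.
- Section 8.7, item 2, rests on the investigator's view, "Discontinuation of treatment due to an adverse event in the opinion of the investigator or the subinvestigator", or on the protocol's own discontinuation criteria, which for this event lead back to Table 8.f.
- Table 8.h makes other non-hematologic toxicity of Grade 3 or higher a suspension criterion, but for TAS-102 only.
- The DLT rules in Section 8.9 concern phase I, Course 1, and feed cohort decisions. They set no re-exposure rule for the individual subject.
- Section 8.0 refers sites to the package insert, whose content is not in the documents.

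**5. Size.** Table 4.c (Japanese surveillance), infusion reaction of Grade 3 or higher:
- Monotherapy: 1 / 1,254 = 0.080%. Expected in 52 subjects: 52 × 1/1,254 = 0.04 (exact 95% interval 0.001 to 0.23).
- With chemotherapy: 5 / 1,831 = 0.273%. Expected in 52: 52 × 5/1,831 = 0.14 (0.05 to 0.33).
- Chance of at least one in 52, 1 − (1 − p)^52: 4.1% and 13.3%.

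These cover reactions of any kind at any infusion.

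**The case against.** The strongest objection is that no experienced site would read the table this way. The row is unqualified, Section 9.2.5 looks for infusion reactions throughout, investigators can always suspend or stop, and Section 8.0 adds: "See the latest package insert for details and handling of each drug". Much of this stands. It is why the point is a wording correction of low severity. It does not remove the mismatch, because every fallback within the documents is discretionary or circular, and a mandatory rule should not depend on readers ignoring its definition.

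Three stronger inferences are tempting and are not supported:

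- *That the three-asterisk footnote permits restarting panitumumab after a Grade 3 reaction.* Its resumption sentence names no grade. But the row already forbids resumption at Grade 3 or higher, and the following sentence names Grades 1 and 2. A course is the two-drug cycle (Section 8.2), and under Section 8.1 one drug continues when the other meets its stopping criteria, so resuming the course need not mean resuming panitumumab. The sentence could be clearer; it does not override the row.
- *That Section 8.12 permits it.* Under allergic reaction, that section says: "Careful administration of panitumumab by slowing the infusion speed may be considered". It gives no grade, but it is recommended supportive care. Section 8.2 sends the reader to 8.3, 8.4 and 8.5 for administration rules.
- *That two sites could act differently with neither deviating.* Without the package insert this cannot be established.

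**Conclusion.** The point holds for the two-asterisk footnote. As written, the definition is narrower than the rule it serves, and Grade 3 or higher chills, fever or dyspnea from Day 15 of Course 1 onward, not judged allergic or anaphylactoid, falls outside the mandatory stop.

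The figures in step 5 are a ceiling in kind, since the uncovered events are a subset of those counted. They rest on 1 and 5 observed events, on regimens other than this combination, and on a surveillance definition of infusion reaction that the protocol does not give.

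A reader might try to size the gap by assuming a share of reactions after the first infusion. At an assumed 10% to 50%, that gives 0.10 × 0.041 = 0.004 to 0.50 × 0.142 = 0.07 events. The documents give no such share, and the result still includes allergic and anaphylactoid reactions that are covered on the reading taken here. It is at most an upper bound under an assumption. Nor should 11 of 12 planned infusions be read as a share of events.

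**What to change.** In the two-asterisk footnote to Table 8.f, replace the closing time limit with: *during or within 24 hours after any panitumumab infusion*. This settles which infusions are covered, whichever reading a site had adopted.

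As a clarification only, begin the resumption sentence of the three-asterisk footnote with *For Grade 1 or 2 reactions*. Optionally, add *after a Grade 1 or 2 reaction* to the panitumumab sentence under allergic reaction in Section 8.12.

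The cost is one phrase in a table footnote, up to two further short phrases if the clarifications are taken, and a note to sites. No visit, test or data item is added.

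### Table 8.f rules out resuming panitumumab after a Grade 3 or higher infusion reaction, but the footnote on that row allows resumption with no grade limit and does not say which drug it means

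*Protocol*

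**What the plan says.** Table 8.f (Protocol Section 8.5.1) lists events that change panitumumab dosing. Its action column is headed "Dose adjustment for the next dose of panitumumab". The row "Infusion reaction (reaction from injection" has Grade 3 or higher in the grade column and "Discontinuation (no resumption" as the action.

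The row label carries two footnotes that appear on no other row:

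- Footnote ** defines the event: "Allergic reaction, anaphylactoid reaction, and chills, fever, and dyspnea occurring within 24 hours after the initial dose". It names no grade.
- Footnote *** has three sentences. The first: "If infusion reaction is observed, immediately discontinue administration". The second: "The course may be resumed at the discretion of the study site". The third begins "In the event that Grade 1 or 2 infusion reaction occurs during infusion, careful administration will be allowed" and goes on to supportive therapy or a slower infusion when the subsequent course is given. Only the third names a grade.

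Section 8.12, under allergic reaction, says: "Careful administration of panitumumab by slowing the infusion speed may be considered". It also names no grade.

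Both versions of the protocol in the file carry the same row, footnotes and Section 8.12 text.

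**The concern.** The row and its footnote can be read as opposite instructions for the same event. The row makes the stop of panitumumab final for Grade 3 or higher. The footnote's second sentence leaves resumption to the site, follows directly on a sentence about any observed infusion reaction, and has no grade limit of its own.

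The stake is the individual patient. Table 10.b describes Grade 3 as severe or medically critical and Grade 4 as life-threatening, so this table would be consulted during or just after a dangerous event. The phase II part plans approximately 30 sites. There is a smaller bookkeeping stake: Section 14.1.3 requires every protocol deviation to be recorded, and a site that relied on the footnote might not recognise resumption as one.

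**Working it through.** The plan gives no figure for this point, so the main check is to set the texts side by side. A short calculation then shows how often the conflict could arise.

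**1. Is the row's action a permanent stop of panitumumab?** Yes. The column concerns the next panitumumab dose. The same no-resumption wording marks the last step of the dose ladders in Tables 8.g and 8.j. Table 8.f uses a different action, stopping all protocol treatment, for pulmonary fibrosis. The infusion reaction row therefore ends panitumumab and does not by itself end TAS-102.

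**2. Does the resumption sentence cover Grade 3 or higher?** The text leaves it open.

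| Sentence in footnote *** | Grade stated | Effect |
|---|---|---|
| First | none | stop administration at once |
| Second | none | the course may be resumed, site decides |
| Third | 1 or 2 | careful administration at the subsequent course |

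The grade limit enters as a new condition in the third sentence. Nothing carries it back to the second, and the footnote is attached to a row defined as Grade 3 or higher.

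**3. Which drug is meant by the course?** Section 8.2 defines a course as 28 days of the two-drug regimen. Section 8.4 lets a course run from the TAS-102 start day when panitumumab is postponed or discontinued, so a course can proceed without panitumumab. That supports reading the sentence as TAS-102 alone. Against it, the footnote sits in the panitumumab table and follows an instruction about administration during an infusion reaction. Its third sentence speaks of infusion speed, which can only concern panitumumab because TAS-102 is oral. Section 8.1 also makes continuing the other drug the default, not a site option. Neither reading is stated.

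**4. Does Section 8.12 resolve it?** No. It allows slower panitumumab infusion after an allergic reaction at any grade, while footnote ** counts an allergic reaction as an infusion reaction, at least within 24 hours of the initial dose. A Grade 3 allergic reaction in that window falls under both the row and Section 8.12.

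**5. How many subjects?** Let p be the rate per subject and n the number of subjects. Expected cases = n × p. Chance of at least one = 1 − (1 − p)^n, taking subjects as independent.

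Inputs: n = 52 (target) or 58 (maximum), from the Study Summary. For Grade 3 or higher, p = 5/1,831 = 0.00273 (Table 4.c, panitumumab plus chemotherapy).

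- n = 52: 52 × 0.00273 = 0.14 expected; 1 − (1 − 0.00273)^52 = 0.13.
- n = 58: 58 × 0.00273 = 0.16 expected; 1 − (1 − 0.00273)^58 = 0.15.

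Other rates in the protocol give a range. Table 4.a (FOLFOX4 plus panitumumab) has 2/322 = 0.0062, hence 0.32 expected in 52 and 0.36 in 58. Table 4.c for panitumumab alone has 1/1,254 = 0.0008, hence 0.04 expected in 52. Every source gives fewer than one expected case. For reactions of any grade, 30/1,831 = 0.0164 gives 0.85 expected in 52 and a chance of 0.58 of at least one.

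**The case against.** The strongest reply is that the markers sit on the item name, not on the grade or action cell. Footnote ** defines the term. Footnote *** then gives general handling text and expressly addresses Grade 1 or 2, which would be out of place in a note confined to Grade 3 or higher. On that view the row is the specific rule for Grade 3 or higher and prevails over a general sentence. Alternatively, the course means TAS-102, and there is no conflict. Section 8.0 also refers sites to the package insert for handling each drug, so practice cannot be judged from Table 8.f alone.

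Both milder readings are plausible, and either may be what was intended. But the protocol states neither, and a site would have to infer the answer. That is why the point is an inconsistency the text leaves unresolved, and not proof that the protocol permits resumption after a Grade 3 or higher reaction.

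A reader might infer two stronger things. One is that a site resuming panitumumab and a site stopping it would both be following the protocol. The documents do not support this: resuming panitumumab after a Grade 3 or higher reaction goes against the row's explicit words, whatever the footnote was meant to say. The other is that discontinuation and dose-intensity results (SAP Section 7.2.3) would become inconsistent. With about 0.14 expected cases in 52 subjects, any effect on those summaries would be negligible.

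**Conclusion.** The inconsistency is real on the printed text. The infusion reaction row forbids resuming panitumumab at Grade 3 or higher. Its own footnote allows resumption without naming a grade or a drug, and Section 8.12 adds an ungraded option for an overlapping event. It deserves correction because of what a misreading could mean for one patient, not because of its frequency.

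The expected count is about 0.14 Grade 3 or higher cases in 52 subjects, with about a 13% chance of any; the protocol's other rates put the expected count between about 0.04 and 0.36. This assumes that rates seen with panitumumab alone or with other chemotherapy carry over to the TAS-102 combination, for which Section 4.2 reports no clinical efficacy data and the protocol gives no infusion reaction rate. The primary endpoint, its test and the sample size do not depend on the point.

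**What to change.** Reconcile the infusion reaction row of Table 8.f, footnote *** and the allergic reaction entry in Section 8.12. The revised text should state:

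- to which grades the resumption sentence applies;
- which drug or drugs are meant by the course;
- how the Section 8.12 option relates to events that also meet the footnote ** definition.

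The clinical team must decide the rule; no view is taken here on what it should be. The cost is a short protocol clarification and notice to sites. No analysis, sample size or data collection changes.
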